7.3 Clinical Tests

The only mandated clinical tests are:

- Albumin
- C-reactive protein (CRP)

These are to calculate mGPS for the patients at baseline and at the three and six month follow-up assessment (see Appendix 3).

7.4 Concomitant Medication

Details of all medications including planned and already commenced treatments will be collected at baseline and any changes to medication and treatments recorded during follow-up ad collected on the CRF.

No restrictions are placed on medications; this includes (using the cancer treatment example) challenges and re-challenges for chemotherapy, and all instances of radiotherapy administered to the patient throughout the duration of the trial; including all symptom control medications.

8 PATIENT REPORTED OUTCOMES

Patients will be asked to complete a number of questionnaire at different time points (as detailed in Table 1 and 2) that will document factors that may influence:

- Decision to continue to the RCT (feasibility only)
- Acceptability of the questionnaires (feasibility only)
- Psychological adjustment
- Quality of life
- Holistic needs
- Cognitive status
- Healthcare resource usage

The questionnaires are briefly described in Appendix 8.

Questionnaires should be completed in clinic and returned to the Trial Office by the site research team.

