2.1.3 Cost-effectiveness

- What are the current costs to the NHS in advanced NSCLC of anti-cancer treatments in hospital, for patients receiving SPC and for patients being managed at home by primary care?
- Does early referral to SPC lead to a shift in resource usage and costs from hospitals to other sectors and what are the overall savings to the NHS?
- Is early referral to SPC associated with a change in quality-adjusted life years (QALY) and is it cost-effective when compared with usual care?
- How can lessons about cost-effectiveness learnt from advanced NSCLC be applied elsewhere in cancer and chronic disease management?

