2.2.2 Randomised Controlled Trial Outcome Measures

The primary objective is to compare the two treatment arms in terms of the two co-primary outcome measures:

- (i) Global Health Status Score (GHSS) at three months post randomisation, and
- (ii) Quality-Adjusted Survival time (QAS) over six months

Secondary outcome measures:

- Overall survival
- Anxiety/depression
- Pain
- Quality of Life
- Cost-effectiveness
- Resource use
 - Days spent in hospital/hospice
 - Admission to an Intensive Therapy Unit (ITU)
 - Use of medical interventions in last month of life (see Appendix 1 for definitions)
 - Use of cardio-pulmonary resuscitation (CPR)
 - Compare the arms of SPARC sub-randomisation in the early palliative care group to see if HNA as an intervention is associated with better outcomes

The following will be measured from trial entry at each clinic visit the patient attends until the end of the trial or death:

- Health related quality of life using EQ-5D-5L and European Organisation for Research and Treatment of Cancer (EORTC) QLQ C30/LC13/BM22
- Hospital Anxiety and Depression Scale (HADS)
- HNA using SPARC (see Appendix 2)
- Modified Glasgow Prognostic Score (mGPS) (see Appendix 3)
- Nurse-rated and patient-rated ECOG
- Montreal Cognitive Assessment scale (MoCA) (see Appendix 4)

Additionally carers will receive:

- Short form-12® (SF-12®) health related quality of life questionnaire
- Family caregiver satisfaction of palliative care services questionnaire (FAMCARE-2)
- The CODE™ instrument

The modified Glasgow Prognostic Score will be used primarily as a prognostic and stratification measure at baseline. It will be repeated again at the key primary end-points of three months and six months to test for its utility as a prognostic score later in the disease ^{[7],[8]}.

In order to control for effects of co-morbidity on patients' physical condition and holistic needs, the Scottish Lung Cancer Co-Morbidity Index (see Appendix 5) will also be used at baseline^[9]. Neither this co-morbidity index nor the mGPS are outcome measures but do represent important potential antecedent variables which could influence symptoms and other holistic needs as well as survival, so will be used in the statistical analysis to help explain variations in the patients' outcomes.

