7.2.2.2 Follow-up Assessments

The patient should be followed up at least once per month for six months. Patients being treated every third week (for example those receiving chemotherapy) will be seen every three weeks while on treatment. The patient's visits should be organised to correspond with their treatment visits where possible.

The following should be assessed at each visit (be that three weekly of four weekly):

- Disease status
- ECOG status (see Appendix 6)

Page | 17 of 64 Version 1.0a, 8 Apr 2016

^{*} Please note: mGPS must be performed prior to randomisation, as this is required to assess eligibility.

Please note: A copy of SPARC should be sent to the patient's palliative care team with the referral letter, the original should be returned to the Trial Office and a copy retained in the ISF

Concomitant medication review

The patient should be asked to complete the following during the clinic appointment:

- Appropriate Follow-up Patient Questionnaire Booklet
- SPARC questionnaire (only if randomised to Arm B2)

In addition to the above, at three and six month assessments, the following must also be assessed:

- mGPS (see Appendix 3 and Section 7.3)
- MoCA (see Appendix 4)

The carer should be asked to complete the Carer Questionnaire Booklet *.

* Please note: If the trial registered carer is not accompanying the patient, please send the carer questionnaire booklet home with patient so that the carer may complete and return it to the site research team at the next follow-up clinic visit.

Completed questionnaires booklets and forms should be returned to the Trial Office with the patient's completed diary sheets.

Please note: The patient may require a new Patient Diary after their six month assessment visit.

The following information will be collected on the CRF at all follow-up visits:

- Treatment details
- Response to treatment (as per local practice)
- Details of relapse/progression
- Hospital admissions, including duration and reason for admission
- · Details of patient referral to the SPC team
- Resource use (see Appendix 1 for list of medical interventions)

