9 CARER REPORTED OUTCOMES

Dependent upon consent, patients' primary informal carers will be asked to complete carer-specific questionnaire booklets as detailed in Tables 1 and 2. A brief description of the questionnaires and booklet contents can be found in Appendix 9.

The questionnaires will be given to carers at baseline by the research staff in the clinic, and collected back on completion and returned to the Trial Office. If the carer wishes to complete the form at home, they may return the completed form directly to the Trial Office in the pre-paid envelope provided.

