19.2.2.1 Primary Outcome Measures

Global health status score: The two treatment groups will be compared in terms of this outcome measure at three months using a t-test. It is recognised that there will be some variation in the timing of the QoL assessments and a window of two weeks either side of the planned three month assessment will be acceptable. This part of the analysis will only be carried out in those patients who are alive and well enough to complete a questionnaire at three months (i.e. a complete case analysis) and therefore it is a conditional analysis but it will be intention-to-treat in the sense of including patients under their randomised allocation.

QAS time: Treatment groups will be compared using a t-test. The advantage of this analysis is that it is intention-to-treat, dealing with missing data due to death and dropout and therefore including all randomised patients in the analysis.

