19.2.5.1 Global Health Status Score

Assuming a median survival time in these patients of six months and an exponential distribution, it is expected that 70% of randomised patients will be alive at three months. Experience in the BTOG2 trial shows that we would expect high compliance in these remaining patients, so we assume a further 5% dropout for reasons other than death, giving a total loss of 35% of randomised patients. From literature, GHSS in patients with metastatic NSCLC is 58.8 with standard deviation of 23 points and data from the stage IV patients in the BTOG2 trial shows similar values with a mean GHSS at baseline of 61.5 and standard deviation (SD) of 23. A difference of seven points between treatment groups at three months, which is a standardised effect size of 0.3, is considered to be realistic and clinically relevant. Assuming a 5% two-sided significance level and 80% power the analysis requires a total of 342 patients to detect this level of difference and thus 525 randomised patients. For 90% power the analysis requires a total of 456 patients and thus 700 randomised patients.

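### Patient booklets carrying GHSS and EQ-5D-5L are placed in clinic with no stated fallback for a surviving patient who cannot attend, so such patients are lost from the three-month GHSS analysis and need imputed values in QAS

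*Protocol*

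**What the plan says.** **Patients.** Section 8: "Questionnaires should be completed in clinic and returned to the Trial Office by the site research team". Section 7.2.2.2, for RCT follow-up: "The patient should be asked to complete the following during the clinic appointment"; the booklet is then listed. The feasibility study has the same instruction in section 7.1.1.2. Section 2.2.2 says the EQ-5D-5L and EORTC instruments are measured "at each clinic visit the patient attends until the end of the trial or death". No section states another route for the patient booklet.

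**Carers.** Section 9: "If the carer wishes to complete the form at home, they may return the completed form directly to the Trial Office", with a pre-paid envelope supplied. Section 7.2.2.2 also sends the carer booklet home with the patient when the carer has not come to clinic.

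**Interviews.** Section 7.2.3 lets patients choose a telephone, home or site interview.

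**Analysis.** Section 19.2.2.1 restricts the GHSS t-test to patients "who are alive and well enough to complete a questionnaire at three months (i.e. a complete case analysis"), within two weeks either side of month three. For QAS, section 19.2.1.1 sets values to zero from death and imputes missing ones, and section 19.2.2.1 keeps all randomised patients.

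**Sample size.** Section 19.2.5.1 takes 70% as alive at three months, "so we assume a further 5% dropout for reasons other than death", and arrives at 342 analysed and 525 randomised for 80% power.

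**Progression target.** Section 19.1.1 sets three-month GHSS completion at 80% of surviving patients.

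**The concern.** The eligible population includes ECOG 3, which Appendix 6 describes as limited self-care with more than half of waking hours in bed or a chair. Assumed median survival is six months, and section 7 notes that SPC comes from a hospice at some sites. Some patients at month three may be able to complete a short form where they are but unable to travel. Followed as written, the protocol never offers them the form.

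For GHSS, a set meant to be survivors well enough to answer becomes in practice survivors well enough to attend. For QAS, utilities must be imputed for patients who are probably among the sickest, and imputation from those who attended may then be too favourable. An analysis plan cannot recover a form that was never offered.

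The loss could also differ between arms. The trial is unblinded, SPC is sometimes delivered outside the hospital, and section 2.1.3 asks: "Does early referral to SPC lead to a shift in resource usage and costs from hospitals to other sectors". If attendance shifts with allocation, the GHSS comparison loses some of the protection of randomisation.

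**Working it through.** **1. The planned GHSS sample size**

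Inputs (section 19.2.5.1): difference 7 points, SD 23, two-sided 5%, 1:1 allocation, total loss 35%.

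- Normal approximation: n per arm = 2 × (1.96 + 0.84)² × (23/7)², giving 340 in total. The t-test gives 341 before rounding up to equal arms, hence 342.
- Randomised: 342 / 0.65 = 526, against 525 stated. This reproduces within rounding.
- Exponential survival with a six-month median: 0.5^(3/6) = 0.707, which matches the stated 70%.

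**2. Completion the plan requires among survivors**

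- Survivors at three months: 525 × 0.70 = 367.5.
- Required completion: 342 / 367.5 = 93%. Equivalently, 65% / 70% = 93%. The allowance for every non-death cause of a missing form is thus about 7% of survivors.

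**3. Power if completion is lower**

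Power ≈ Φ(d × √(n/4) − 1.96), where n is the total analysed and d is 7/23 = 0.304 or the rounded 0.30 that the protocol also states. The table gives t-test values.

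| Survivors completing | Analysed | Power, d = 0.30 | Power, d = 7/23 |
|---|---|---|---|
| 93% (plan) | 342 | 79% | 80% |
| 85% (assumed) | 312 | 75% | 76% |
| 80% (section 19.1.1 target) | 294 | 73% | 74% |

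At 80% completion, keeping 342 analysed would need 342 / (0.70 × 0.80) = 611 randomised. The 85% row is an assumption. The 80% row uses the protocol's own threshold. Neither says how much of the shortfall is due to the clinic setting.

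**4. Possible bias in the GHSS difference**

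Let m be the proportion of survivors without a score in an arm, and G the mean gap by which completers outscore non-completers, taken as equal in both arms. The completers' mean exceeds the mean of all survivors in that arm by m × G, so the arm difference B − A shifts by (m_B − m_A) × G.

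The documents give neither quantity. For illustration only:

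- Equal loss in both arms: shift 0, whatever G is.
- 5 points of percentage difference and G = 15: 0.05 × 15 = 0.75.
- 10 and G = 20: 0.10 × 20 = 2.0, which is 2.0 / 7 = 29% of the target difference.
- 15 and G = 25: 0.15 × 25 = 3.75.

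The illustrative range is 0 to 3.75 GHSS points, in either direction.

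**5. QAS**

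All randomised patients are included, so the analysed number does not fall. The effect is on how much of each utility curve is imputed. The documents give no figure for this.

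**The case against.** - **The wording is advisory.** The protocol says should, and nothing voids a booklet completed elsewhere. Section 15.1 asks only that participant-reported forms be completed on paper and returned, and section 7.2.2.3 does not repeat the clinic wording for long-term follow-up. This stands: it is wrong to read the text as a prohibition. But an unwritten exception left to each site in an unblinded trial is not a controlled fallback.
- **Nobody leaves QAS.** A reader might infer that these patients drop out of both co-primary outcomes. Sections 19.2.1.1 and 19.2.2.1 do not support that: missing utilities are imputed and everyone randomised is analysed. The exclusion applies to GHSS alone.
- **Differential loss is not shown.** A reader might infer that Arm B will attend less. The aims in section 2.1.3 are open questions. SPC is added to standard oncology or respiratory follow-up (sections 3.2 and 7.2.1.2), both arms share one visit schedule, and section 7.3 mandates blood tests at three and six months for all. Differential loss remains plausible, without a stated size or direction.
- **Part of the loss is not recoverable.** Some patients too ill to travel will be too ill to complete a form anywhere, and the 5% allowance draws on observed compliance in an earlier trial. Both points stand, so the power figures cannot be charged wholly to the clinic setting.
- **The feasibility stage will measure completion.** It will, and section 3.1.1 allows amendments afterwards. But it uses the same in-clinic route, so it would reveal a shortfall without supplying or testing a fallback.
- **Clinic completion and the carer route have reasons.** Section 7.2.2.1 has staff explain the forms and check them for completeness and dates. Carers have no scheduled visits of their own. The contrast is therefore not a contradiction. It only shows that a home route is already workable in this trial.

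**Conclusion.** The point holds as a gap in data collection. The protocol places the patient booklet in clinic and states no alternative for a living patient who cannot attend. Such a patient is excluded from the complete-case GHSS test and needs imputed EQ-5D-5L values in QAS.

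The firm figures are that about 93% of survivors must complete for the planned GHSS power, and that at the protocol's 80% target about 294 are analysed with power about 73–74%. These rest on the protocol's survival, SD and effect-size assumptions. The share attributable to the clinic setting is unknown.

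That the missing scores depend on illness is probable. That the loss differs by arm is possible but unsupported by any figure, so the bias illustration of 0 to 3.75 points should be read as a range containing zero. The change is worth making because the gap affects a co-primary outcome and is cheap to close.

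**What to change.** In sections 7.2.2.2 and 8, and in section 7.1.1.2 so that feasibility completion rates apply to the RCT:

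- Keep completion at the clinic appointment as the default.
- At three and six months at least, require sites to offer a patient who cannot attend the same booklet at home or in the hospice, completed within the visit window and returned in a pre-paid envelope.
- Record place of completion on the form.
- Bring the measurement sentence in section 2.2.2 into line, so that it no longer ties these instruments to visits attended.

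**Cost.** Protocol wording, one extra field, and envelopes of the kind already supplied to carers. No change to treatment, outcomes or sample size. The downside is less staff checking of forms and a mix of completion settings, which the recorded field would let the analysis describe by arm.

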9 CARER REPORTED OUTCOMES

Dependent upon consent, patients' primary informal carers will be asked to complete carer-specific questionnaire booklets as detailed in Tables 1 and 2. A brief description of the questionnaires and booklet contents can be found in Appendix 9.

The questionnaires will be given to carers at baseline by the research staff in the clinic, and collected back on completion and returned to the Trial Office. If the carer wishes to complete the form at home, they may return the completed form directly to the Trial Office in the pre-paid envelope provided.

10 QUALITATIVE INTERVIEWS WITH PATIENTS AND CARERS

During the feasibility study a nested qualitative trial will be used to assist in the appropriate development of the RCT protocol (see Section 3.1.1). Patients and carers who choose to participate will be approached directly by the by the Qualitative Researchers in Sheffield as described in Section 7.1.2.

A mixture of face-to-face and telephone interviews will be undertaken. Face-to-face interviews will be used where possible, but in recognition that it may sometimes be difficult to organise these a telephone interview will be arranged if necessary. Interviews will be based upon a semi-structured approach. A total of 15 interviews (five patients, five carers and five clinical staff) at each site will be undertaken (n=45). Patients and carers will be interviewed between six weeks and three months from registration, clinician interviews will be carried out throughout the feasibility study.

A second nested trial will take place during the RCT (see Section 3.2.1). During the RCT, semi-structured face-to-face or telephone interviews will be undertaken with 45-50 patients and their carers where appropriate at approximately three and six months post randomisation. These interviews will be audio recorded. Four centres which form part of the RCT will be purposively sampled as the focus for the qualitative study; these four will include two rural and two urban settings. Patient/carer age (<50, 50+) and gender will be used as criteria for selection and at least three participants in each site will be recruited to each sub-group (12 per site selected for this part of the study n=48). Interviews will also be performed with clinical staff. In each of these four sites four clinical staff from each will be interviewed once during the study between three and four months after recruitment has begun, either face-to-face or over the telephone. These will be purposively sampled to ensure that medical and nursing staff are included. These interviews will be audio recorded.

Patients and carers will be sampled as above and approached by the site research team with a view to taking part in a qualitative interview. Those who express an interest will be provided with an information sheet and consented as detailed in Section 5.2. If appropriate a convenient appointment will be arranged by the Qualitative Researchers in Sheffield as described in Section 7.2.3.

The nature of the interview will be determined at the conclusion of the feasibility study although it is anticipated that interviews will initially be based on the topic guide included in Appendix 10.

Interviews will be transcribed verbatim. These data will be analysed using Framework Analysis^[10] of which there are six stages:

- 1. Familiarisation: reading transcripts and fieldwork notes.
- 2. Identifying recurring themes: beginning to develop a working framework of the important themes and patterns within the data.
- 3. Indexing: applying a numerical code to each theme and using this to label transcripts. It may also be the case that amendments to the original framework are made at this stage.
- 4. Pilot charting: creating a chart/matrix using the framework and initial transcript data.
- 5. Charting: complete a matrix using full data set.
- 6. Interpreting: making use of the completed framework to understand and interpret patient and care experiences of early SPC referral.

11 HEALTH ECONOMICS

The feasibility study will measure the feasibility of collecting a range of data on resource usage in the three cohorts. The RCT will apply the acceptable measures at three to four weekly intervals.

11.1 Feasibility Study

We will use the feasibility study to pilot the Patient's Costs questionnaire which will be administered to patients and their carers. We have used the DIRUM database (Database of Instruments for Resource Use Measurement) and existing resource questionnaires to design a draft resource use questionnaire and this will be piloted for acceptability in the feasibility study^[11]. As part of the piloting we will test the acceptable recall period for patients and the frequency of administration. Initially, the questionnaire will be administered at every assessment point and the change in resource use over time will be reviewed.

11.2 Randomised Controlled Trial

The primary analysis will present costs per QALY from an NHS and social care perspective in accordance with NICE guidelines^[12]. Resource use on inpatient and out-patient hospital attendances, treatments and procedures will be collected from routine patient records. GP visits (home and surgery), district nurse visits and other specialist care received in primary care will be collected via the resource use questionnaire developed in the feasibility study. The questionnaire will also collect information on carers' time and loss of productivity which will be included in secondary analysis of costs per QALY to the NHS and society. Unit costs will be derived from appropriate national sources and will include; NHS reference costs, Personal Social Service Research Unit costs and the Office of National Statistics^{[13],[14],[15]}.

QALYs over six months will be calculated using the area under the curve formed by the longitudinal measures of the utility scores from EQ-5D-5L within six months, with all values from death onwards represented by '0' and imputation used to complete the curves where data are missing.

It is possible to derive utilities for the measurement of QALYs from both the EORTC ^[16] and the EQ-5D-5L. We will present costs per QALY results for the main analysis for EQ-5D-5L in accordance with NICE guidelines and present cost per QALY results using EORTC in sensitivity analysis. Results will be presented as incremental costs per QALY and will adjust for censoring using Lin's methods^[17] for costs and QALY data, results will be presented in the net-benefit framework and will allow for uncertainty using bootstrapping and probabilistic sensitivity analysis.

